6.0 STUDY TREATMENT

Patients will be randomly assigned to receive double-blind study medication (either ensifentrine or placebo) administered using the inhaled route via a standard jet nebulizer (Section 6.2.2) supplied by the Sponsor.

In this protocol the terms ‘investigational product,’ ‘double-blind study medication,’ and ‘blinded study medication’ are the same and refer to the blinded nebulized study medication.

6.1 Administration of Blinded Study Medication

6.1.1 Dosing in the Clinic

The Clinic Visit *MUST BE RESCHEDULED* within 3 days of the scheduled visit if any of the following apply:

- If the rescue medication or maintenance LAMA or LABA medication are not withheld for the time intervals defined in Section 6.7.2.
- If the morning dose of blinded study medication is not withheld.

Dosing Environment

- To avoid cross-contamination, blinded study medication dosing must be conducted in a shielded and well-ventilated environment.
- Patients may be in the same room as other patients who are being dosed on the same day if separated by a partial partition or curtain and if other patients and other staff members cannot visualize the study medication administration by the blinded study site staff member. These measures are in place to protect study medication blinding.

Designated Unblinded Site Staff Member

To maintain the treatment blind, each site will designate an unblinded site staff member not associated with study conduct to administer in-clinic doses.

Dosing Visit Schedule and Time(s) of Day

Coordination of the timing of spirometry and in-clinic dosing with blinded study medication is critical. See Section 1.4, for the Schedule of Spirometry and In-Clinic Dosing with Blinded Study Medication.

Blinded Study Medication Administration

A new PARI LC Sprint® jet nebulizer (study supplied nebulizer), with a PARI Vios® PRO Aerosol Delivery System PARI BOY® compressor or equivalent (study supplied

compressor) will be dispensed to the patient and used to dose the blinded study medication in the clinic and at home.

- Blinded study medication will be administered by inhalation of an aerosol generated by the reusable study supplied nebulizer attached to a study supplied compressor.
- The unblinded site staff member should follow the nebulizer Set-Up instructions provided with the nebulizer and the Pharmacy Manual to prepare and administer the blinded study medication.
- Administration of nebulized blinded study medication will be observed by the unblinded site staff member from start of nebulization until end time of nebulization. The unblinded site staff member MUST administer blinded study medication at all in-clinic dosing times. Patients may be discharged from the clinic after Week 12 assessments are complete to self-administer their evening dose of study medication. If administered in the clinic, the Week 12 evening dose must be administered by unblinded site staff.
- Blinded study medication nebulization time should be approximately 5 minutes and may not exceed 10 minutes.
- The end time of blinded study medication nebulization is when a slight sputtering sound from the nebulizer is heard. This will be considered Time 0 for the purposes of scheduling all post-dose study procedures.
- The date, the start time, and the end time of blinded study medication nebulization will be recorded by the unblinded site staff member in the patient source document and the electronic case report form (eCRF).
- Patients will take their study supplied nebulizer study supplied compressor and instructions home for use during the study. A new study supplied nebulizer(s) will be issued periodically. Only a study supplied nebulizer and a study supplied compressor may be used to administer blinded study medication during the study.

6.1.2 Dosing at Home

Following Visit 1, patients will self-administer their daily morning and evening doses at home at approximately the same times, approximately 12 hours apart, each day for the duration of the study, except for specific clinic visit days when patients will have their doses administered in the clinic.

Prior to Dosing at Home

- Patients in the maintenance LAMA or LABA stratum should take their maintenance LAMA or LABA (and ICS, if applicable) prior to taking blinded study medication.

Blinded Study Medication Administration

- Each patient will follow the Nebulizer Set-Up instructions and blinded study medication label to prepare and self-administer the blinded study medication by inhalation using the reusable study supplied nebulizer attached to the study supplied compressor.

- Blinded study medication nebulization time should be approximately 5 minutes and may not exceed 10 minutes.
- The end time of blinded study medication nebulization is considered to be when a slight sputtering sound from the nebulizer is heard. This will be considered Time 0 for the purposes of scheduling all post-dose study procedures.
- On the evening Prior to the Week 6, Week 12 and Week 24 Visits (or Early Term/Withdrawal visits where 12-hour spirometry will be performed): On a patient paper diary, the patient will record the date, the start time of nebulization, and the end time of nebulization for the evening dose of blinded study medication.

Used Blinded Study Medication

- Patients will be instructed to discard all used ampules of blinded study medication and the open foil pouches that contained the used ampules at home.

Unused Blinded Study Medication

- Patients should be instructed to bring all unused blinded study medication to the clinic at each clinic visit for collection and assessment of medication compliance by the unblinded site staff member.
- If a foil pouch is opened but the blinded study medication is not opened/not used, the patient should seal the opened foil pouch (eg, tape) before returning it to the clinic.

6.2 Investigational Product/Blinded Study Medication

Investigational product/blinded study medication is described in Table 5.

Table 5: Investigational Product/Blinded Study Medication Details

| Name: | Ensifentrine | Placebo |
|-------------------------|--|--|
| Dosage Formulation: | Nebulizer suspension | Nebulizer solution |
| Unit Dose: | 3 mg | 0 mg |
| Concentration (mg/mL) | 1.2 mg/mL | 0 mg/mL |
| Route of Administration | Inhalation | Inhalation |
| Dosing Instructions: | 1 ampule (2.5 mL) per dose | 1 ampule (2.5 mL) per dose |
| Manufacturer | The Ritedose Corporation, Columbia, SC, USA | The Ritedose Corporation, Columbia, SC, USA |

The ensifentrine formulation is a sterile suspension of micronized ensifentrine [REDACTED] and supplied as a 2.5 mL nominal fill in single unit-dose low density polyethylene (LDPE) translucent ampule overwrapped in a foil pouch.

The placebo is the same as the ensifentrine suspension except that the active ensifentrine ingredient is omitted, [REDACTED]

[figure not shown]
and is also supplied as a single unit-dose LDPE translucent ampule overwrapped in a foil pouch.

Both ensifentrine and placebo are manufactured using aseptic manufacturing techniques in accordance with Good Manufacturing Practice GMP guidelines and will be provided to the sites as patient kits.

6.2.1 Blinded Study Medication Dispensing and Formulation Information

Patients will be dispensed blinded study medication kit(s) as per the schedule outlined in the SoA with one exception. If a patient is unable to attend a scheduled visit due to disaster, the instructions for blinded study medication dispensing as outlined in Section 8.6 should be followed.

The blinded study medication formulation constituent and concentrations are described in Table 6.

A table with a header row and approximately 10 data rows. The entire table content is obscured by black redaction boxes. The table structure appears to have two main columns, with the right column being significantly wider than the left column.

6.2.2 Medical Devices

1. No Sponsor manufactured medical device is used in this study.
2. Other medical devices provided for use in this study are:
 - PARI LC Sprint nebulizer
 - PARI Vios PRO Aerosol Delivery System, PARI BOY compressor or equivalent
3. Instructions for medical device use are provided in the package insert.
4. Information on medical device incidents and reporting is provided in Section 8.7.8.

6.3 Preparation/Handling/Storage/Accountability

1. Blinded study medication should be stored below 25°C (77°F) and should not be frozen.
2. An investigator or designee must confirm appropriate temperature conditions have been maintained during transit for all blinded study medication received and any discrepancies are reported and resolved before use of the blinded study medication.
3. All blinded study medication must be stored in a secure, environmentally controlled, and monitored (manual or automated) area in accordance with the labeled storage conditions with access limited to the Investigator and authorized study center staff.
4. The temperature should be monitored, and logs maintained in areas where blinded study medication is stored. If temperature conditions have been compromised or any blinded study medication has not been stored appropriately, this should be documented, and the blinded study medication quarantined until the Sponsor has been notified and confirmed whether it may be used.
5. Only patients meeting the Randomization Criteria in the study may receive blinded study medication and only authorized study center staff may supply or administer blinded study medication.
6. The Investigator, institution, or the head of the medical institution (where applicable) is responsible for blinded study medication accountability, reconciliation, and record maintenance (i.e. receipt, reconciliation, and final disposition records).
7. Further guidance and information for the final disposition of unused blinded study medication are provided in the Pharmacy Manual.

The Investigator, a member of the study site staff, the site pharmacist, or pharmacy team member must maintain an adequate record of the receipt and distribution of all blinded study medication using the Drug Accountability Form. These forms must be available for inspection at any time.

6.4 Measures to Minimize Bias: Randomization and Blinding

1. Both ensifentrine and placebo pouches and packaging are identical in appearance.
2. Packaging of both ensifentrine and placebo will have a blinded description applied and all packs will have a unique kit number applied for identification.
3. Deliveries of both ensifentrine and placebo will not indicate the actual product but will instead indicate a blinded description.
4. Patients will be randomized to receive either ensifentrine or placebo using an electronic Interactive Response Technology (IRT). The IRT will not indicate the treatment arm during the randomization process but will indicate the unique kit numbers to be dispensed to the patient.
5. Site staff (both blinded and unblinded) will only have access to blinded reports within the IRT.
6. An unblinded site staff member not associated with study conduct will administer in-clinic doses.
7. If more than one patient will be at the clinic at the same time, they will be shielded from each other to prevent cross-contamination or observance of treatment.

Note: Patients may be aware of the appearance when pouring blinded study medication into the nebulizer. Therefore, they should be instructed not to inform site personnel of the appearance of their blinded study medication. Similarly, study personnel are not to discuss the appearance with patients or other site personnel. Patients will be instructed to return unused blinded study medication (ie, unopened or unused blinded study medication in taped foil pouches) only to the unblinded site staff at their next visit. The investigator will need to confirm and document that the blinding procedures have/have not been maintained for each patient throughout the study. See Data Quality Assurance in Section 11.2).

6.5 Emergency Unblinding

The blind will be broken only if specific emergency treatment would require knowing the treatment status of the patient. If the blind needs to be broken, the Investigator will contact the Sponsor or Medical Monitor as soon as feasible. The Investigator may unblind the blinded study medication immediately if he/she feels it is necessary prior to contacting the Sponsor or Medical Monitor. However, the Investigator should promptly document and explain any premature unblinding to the Sponsor and Medical Monitor. Otherwise, all blinding will be maintained until all queries are resolved and the database is locked.

Unblinding that occurs for any other reason, including unintentional unblinding, will be documented and promptly reported to the Sponsor and Medical Monitor.

6.6 Blinded Study Medication Compliance

The prescribed dosage, timing, and mode of administration may not be changed. Any departures from the intended regimen must be recorded in the eCRFs.

At each visit, prior to dispensing blinded study medication, previously dispensed unused blinded study medication (ie, unopened or unused blinded study medication in taped foil pouches) will be retrieved by the unblinded site staff member and compliance assessed. Patients exhibiting poor compliance as assessed by the number of ampule/foil pouch counts dispensed and returned should be counseled on the importance of good compliance to the study dosing regimen and this counseling should be documented in the patient source document.

Noncompliance is defined as taking less than 70% of blinded study medication during any evaluation period (visit to visit).

6.7 Concomitant Therapy

The Medical Monitor should be contacted if there are any questions regarding concomitant or prior therapy.

6.7.1 Rescue Medication

Study albuterol/salbutamol should be used for rescue use. If study rescue albuterol/salbutamol cannot be dispensed at a scheduled clinic visit, the medication may be dispensed alternatively according to local requirements (Section 8.6). If at any time during the study albuterol/salbutamol is unavailable in a given country or region, the Medical Monitor must be contacted to discuss and approve alternative rescue medication (Section 8.6).

6.7.1.1 Documentation of Rescue Medication Use

- Documentation of albuterol/salbutamol during the 3 months prior to Screening should be recorded on the concomitant medication page of the eCRF along with reason for use, dates of administration (start and end dates), and dosing information (dose and frequency). End date should be documented as “Ongoing.”
- Rescue albuterol/salbutamol used during clinic visits where spirometry will be conducted should be recorded in a module provided in the eCRF for each specific spirometry visit. Details (eg, dose (number of puffs), date, and time of administration) will be recorded.
- Rescue albuterol/salbutamol used at all other times after Screening will be documented in the eDiary (eg, number of puffs per day).
- After Screening, use of Rescue Medication will not be recorded in the concomitant medication page of the eCRF.

6.7.2 Permitted Rescue and Background Medications

Permitted rescue and background medications are provided in Table 7.

Any vaccine that is recommended by the patient’s healthcare provider is permitted during the study (e.g. COVID, influenza, pneumonia), and should be recorded in the eCRF.

Table 7: Permitted Rescue and Background Medications

| Medication | Condition |
|---|---|
| Albuterol/salbutamol | Used as rescue medication as needed during the study. Must be withheld for at least 4 hours prior to spirometry. ¹ Should be withheld for at least 4 hours prior to ECGs. |
| Either LAMA or LABA | Patients entering the study on a maintenance regimen of either LAMA or LABA therapy will be required to remain on that regimen at a stable dose for the duration of the study. Dual LAMA/LABA therapy is not allowed. Stable ICS use is allowed along with a LAMA or LABA maintenance regimen if it was initiated at least 4 weeks prior to Screening. ICS monotherapy is not allowed. Must withhold prior to spirometry: Twice-Daily maintenance LAMA or LABA (or LAMA/ICS or LABA/ICS) for 24 hours, and Once-Daily maintenance LAMA or LABA (or LAMA/ICS or LABA/ICS) for 48 hours, including at Visit 1. ¹ The maintenance LAMA or LABA (or LAMA/ICS or LABA/ICS) therapy should resume once all spirometry for a given visit has been completed. |
| No maintenance or background therapy | Patients entering the study on no maintenance background therapy will not be allowed to initiate background maintenance therapy for COPD (ie, maintenance LAMA or LABA therapy, or ICS therapy) for the duration of the study. |
| Inhaled corticosteroids (ICS) | Stable use of ICS is permitted IF the patient has been taking the ICS at least 4 weeks prior to Screening (Visit 0) AND the patient is also taking maintenance LAMA or LABA. ICS should not be initiated or discontinued during the study. ICS monotherapy and high dose ICS (e.g. >1000 mcg of fluticasone propionate or equivalent) is not allowed. |
| ¹ If the withholding periods are not met the visit should be rescheduled to be held within 3 days of the scheduled visit. Abbreviations: COPD=chronic obstructive pulmonary disease; LAMA= long-acting muscarinic antagonist; LABA= long-acting β 2 agonist | |

6.7.3 Prohibited Medications/Therapy

Prohibited medications and therapies are provided in Table 8.

Table 8: Prohibited Medications/Therapy

| Medication | Time Interval |
|--|--|
| Oral, Systemic or Parenteral Steroid Therapies | 3 months prior to Screening Visit and prohibited during the study. ¹ |
| Antibiotics for lower respiratory tract infection | 6 weeks prior to Screening Visit and prohibited during the study. ¹ Chronic use of antibiotics is not allowed 6 weeks prior to or during the study. |
| Inhaled Corticosteroids (ICS) (e.g. ICS monotherapy and patients in the no maintenance therapy stratum) High dose ICS (e.g. >1000 mcg of fluticasone propionate or equivalent) | 4 weeks prior to Screening Visit and prohibited during the study. |
| Oral leukotriene inhibitors (i.e. montelukast, zafirlukast, zileuton) | 48 hours prior to Screening Visit and prohibited during the study. |
| Theophylline and PDE4 inhibitor (e.g. roflumilast, apremilast, crisaborole) | 48 hours prior to Screening Visit and prohibited during the study. |
| Terbutaline | 1-day prior to Screening Visit and prohibited during the study. |
| Ipratropium (including combinations with albuterol/salbutamol) | 6 hours prior to Screening Visit and prohibited during the study. |
| LAMA/LABA combination products | 4 weeks prior to Screening Visit and prohibited during the study. |
| Nebulized LAMA or LABA or ICS For patients in the no maintenance therapy stratum: For patients in the LAMA or LABA stratum: | 4 weeks prior to Screening Visit and prohibited during the study. 1-week prior to Screening Visit and prohibited during the study (e.g. patient should switch from nebulized to dry powder or metered dose therapy) |
| LAMA Excluded ONLY for patients in the no maintenance therapy stratum | 4 weeks prior to Screening Visit and prohibited during the study. ² |
| LABA Excluded ONLY for patients in the no maintenance therapy stratum | 4 weeks prior to Screening Visit and prohibited during the study. ² |
| Oral beta ₂ -agonists | 1-week prior to Screening Visit and prohibited during the study. |
| 
¹Except for the treatment of COPD exacerbations during the study (Section 11.6). Localized corticosteroid injections (eg, intra-articular and epidural), intranasal and topical corticosteroids are permitted.
 
²Washout of patients on stable background maintenance LAMA or LABA monotherapy for the sole purpose of study eligibility is not recommended.
 
Abbreviations: COPD=chronic obstructive pulmonary disease; ICS=inhaled corticosteroids; LAMA= long-acting muscarinic antagonist; LABA= long-acting β₂ agonist; PDE4= phosphodiesterase 4
 | |

6.7.4 Recording Use of Concomitant Medications

6.7.4.1 *Recording of Rescue Medication and/or LAMA or LABA Medications, and ICS (if applicable)*

- Rescue medication (albuterol/salbutamol) use during the study should be recorded as described in Section 6.7.1.
- Use of LAMA or LABA medications, and ICS (if applicable) during the 3 months prior to Screening should be recorded on the concomitant medication page of the eCRF along with reason for use, dates of administration (start and end dates), and dosing information (dose and frequency).
 - For patients in the maintenance LAMA or LABA therapy stratum, the end date for LAMA or LABA, and ICS (if applicable) should be documented as “Ongoing.”
 - For patients not in the maintenance LAMA or LABA therapy stratum, the actual end date should be documented, if applicable.
- For patients in the maintenance LAMA or LABA therapy stratum, the LAMA or LABA (or LAMA/ICS or LABA/ICS) medication used during the study should be recorded in the eDiary only.
- See Section 8.5.10.2 for information to be collected for PK.

6.7.4.2 *Recording of Medications other than Rescue Medication and/or LAMA or LABA or ICS Medications*

All COPD medications used within 3 months prior to Screening will be recorded in the eCRF. All non-COPD medications will be recorded in the eCRF starting at Screening and changes recorded during the study. Information recorded will include, but may not be limited to items such as:

- Reason for use.
- Dates of administration including start and end dates.
- Dosage information including route, dose, and frequency.

6.7.4.3 *Recording of Medications and Information Specific to the Pharmacokinetic Procedures and Sample Analysis:*

See Section 8.5.10.2 for recording of medications and information specific to the PK procedures and sample analysis.

6.8 Treatment After the End of Study

There are no plans to provide post-study treatment, including study medication for compassionate use following study completion.

At the end of the blinded study medication treatment period (Visit 5 or Visit 9 or early termination), patients may resume conventional COPD therapy as prescribed by the investigator or other physician.

Medications initiated after the end of study treatment should not be entered into the eCRF except for those given for a serious adverse event (SAE).

7.0 DISCONTINUATION OF BLINDED STUDY MEDICATION AND PATIENT DISCONTINUATION/WITHDRAWAL

7.1 Discontinuation of Blinded Study Medication

Patients who permanently discontinue blinded study medication are not required to withdraw from the study unless they test positive for COVID-19 active disease. If a patient must permanently discontinue blinded study medication for reason(s) other than testing positive for COVID-19 active disease, the patient should complete the “Patient Discontinuation/Withdrawal from the Study” assessments described in Section 7.3 as soon as possible. In addition, every effort should be made by the investigator/staff to keep the patient in the study to collect important efficacy and safety data as detailed in Section 7.2.

Circumstances potentially requiring or actually resulting in discontinuation of blinded study medication are described below.

See the SoA (Section 1.3) for data to be collected at the time of treatment discontinuation and follow-up and for any further evaluations that need to be completed.

7.1.1 Does Not Meet Criteria for Randomization

If a patient who does not meet the Randomization Criteria is inadvertently randomized and receives blinded study medication, the Medical Monitor must be contacted and will consult with the Sponsor to determine if the patient may continue, must be discontinued from blinded study medication and/or discontinued from the study.

7.1.2 Liver Chemistry Stopping Criteria

Discontinuation of blinded study medication for abnormal liver function should be considered by the Investigator when a patient meets one of the conditions outlined in Section 11.9 or if the Investigator believes that it is in best interest of the patient.

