11.9 Appendix 9: Liver Safety

Phase III-IV liver chemistry stopping and follow-up criteria have been designed to assure patient safety and evaluate liver event etiology (in alignment with the FDA premarketing clinical liver safety guidance). Phase III-IV liver chemistry stopping criteria 1-5 are defined below. Investigators may at their discretion refer patients meeting liver safety criteria below to a specialist who may determine the appropriate or medically necessary additional or confirmatory laboratory tests or procedures as required by the protocol or otherwise deemed necessary (e.g. liver imaging).

1. ALT \geq 3xULN and bilirubin \geq 2xULN (35% direct bilirubin) (or ALT \geq 3xULN and INR $>$ 1.5, if INR measured).

Note: if serum bilirubin fractionation is not immediately available, withdraw study drug for that patient if ALT \geq 3xULN and bilirubin \geq 2xULN. Serum bilirubin fractionation should be performed if testing is available. If testing is unavailable, record presence of detectable urinary bilirubin on dipstick, indicating direct bilirubin elevations and suggesting liver injury.

2. ALT \geq 8xULN.
3. ALT \geq 5xULN but $<$ 8 xULN persists for \geq 2 weeks.
4. ALT \geq 3xULN if associated with symptoms (new or worsening) believed to be related to hepatitis (such as fatigue, nausea, vomiting, right upper quadrant pain or tenderness, or jaundice) or hypersensitivity (such as fever, rash or eosinophilia).
5. ALT \geq 5xULN but $<$ 8 xULN and cannot be monitored weekly for \geq 2 weeks.

When any of the liver stopping criteria 1-5 is met do the following:

- **Immediately** discontinue blinded study medication/investigational product for that patient.
- Report the event to IQVIA within 24 hours of learning its occurrence.
- Complete the liver event CRF and SAE data collection tool if the event also meets the criteria for an SAE. All events of ALT \geq 3xULN and bilirubin \geq 2xULN (35% direct bilirubin) (or ALT \geq 3xULN and INR $>$ 1.5, if INR measured); INR measurement is not required and the threshold value stated will not apply to patients receiving anticoagulants), termed 'Hy's Law' must be reported as an SAE (excluding studies of hepatic impairment or cirrhosis).

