Note: if serum bilirubin fractionation is not immediately available, discontinue blinded study medication/investigational product for that patient if ALT \geq 3xULN and bilirubin \geq 2xULN. Serum bilirubin fractionation should be performed if testing is available. If testing is unavailable, record presence of detectable urinary bilirubin on dipstick, indicating direct bilirubin elevations and suggesting liver injury.

- Complete the liver imaging and/or liver biopsy CRFs if these tests are performed.
- Perform liver event follow-up assessments and monitor the patient until liver chemistries resolve, stabilize, or return to baseline values as described below.
- Discontinue blinded study medication/investigational product after completion of the liver chemistry monitoring as described below.
- Do not restart investigational product.

In addition, for criterion 1:

- Make every reasonable attempt to have patients return to clinic within 24 hours for repeat liver chemistries, liver event follow-up assessments (see below), and close monitoring.
- A specialist or hepatology consultation is recommended.
- Monitor patients twice weekly until liver chemistries (ALT, AST, alkaline phosphatase, bilirubin) resolve, stabilize or return to within baseline values.

For criteria 2, 3, 4, and 5:

- Make every reasonable attempt to have patients return to clinic within 24-72 hours for repeat liver chemistries and liver event follow-up assessments (see below).
- Monitor patients weekly until liver chemistries (ALT, AST, alkaline phosphatase, bilirubin) resolve, stabilize, or return to within baseline values; criterion 5 patients should be monitored as frequently as possible.

Patients with ALT $\geq 5xULN$ and $< 8xULN$ which exhibit a decrease to ALT $\geq 3xULN$, but $< 5xULN$ and bilirubin $< 2xULN$ without hepatitis symptoms or rash, and who can be monitored for 4 weeks:

- Notify the IQVIA Medical Monitor within 24 hours of learning of the abnormality to discuss patient safety.
- Can continue investigational product
- Must return weekly for repeat liver chemistries (ALT, AST, alkaline phosphatase, bilirubin) until they resolve, stabilize or return to within baseline.
- If at any time these patients meet the liver chemistry stopping criteria, proceed as described above.
- If, after 4 weeks of monitoring, ALT $< 3xULN$ and bilirubin $< 2xULN$, monitor patients twice monthly until live chemistries normalize or return to within baseline values.

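### Protocol 7.1.2 leaves stopping drug to the investigator's consideration where Section 11.9 requires an immediate and permanent stop

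*Protocol*

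**What the plan says.** Protocol Section 7.1.2 is a single sentence under a heading that names the liver chemistry stopping criteria. It reads "Discontinuation of blinded study medication for abnormal liver function should be considered by the Investigator when a patient meets one of the conditions outlined" and continues "in Section 11.9 or if the Investigator believes that it is in best interest of the patient".

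Section 11.9 (Appendix 9) defines five numbered stopping criteria based on ALT, bilirubin, INR, symptoms and whether the patient can be monitored. It then says "When any of the liver stopping criteria 1-5 is met do the following". The first action in the list, with the word *immediately* in bold, is to "discontinue blinded study medication/investigational product for that patient". The last is "Do not restart investigational product".

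The same list contains a stop instruction with different timing: "Discontinue blinded study medication/investigational product after completion of the liver chemistry monitoring as described below".

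Investigator discretion appears once in 11.9, in its opening paragraph: "Investigators may at their discretion refer patients meeting liver safety criteria below to a specialist".

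One group may stay on drug: patients whose ALT was at least 5 but below 8 times the upper limit of normal (ULN), has fallen to at least 3 but below 5 times ULN, whose bilirubin is below 2 times ULN, who have no hepatitis symptoms or rash, and who can be monitored for 4 weeks. For them, 11.9 adds: "If at any time these patients meet the liver chemistry stopping criteria, proceed as described above".

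**The concern.** Section 7.1.2 applies one discretionary verb to two different situations: the patient meets a condition in 11.9, or the investigator judges that stopping is in the patient's interest. Discretion suits the second. For the first it contradicts the appendix that the sentence refers to.

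What is at stake is patient safety and uniform conduct. An investigator following 7.1.2 is asked to weigh a decision that 11.9 has already made. A site that considers the matter and keeps dosing has complied with the main text and breached the appendix. About 151 centers are planned (Protocol synopsis), the SAP (4.1) states that there is no data monitoring committee, and chronic stable hepatitis B or C does not exclude a patient (Protocol 5.2, criterion 12). Site-level liver stopping rules therefore have to be clear.

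**Working it through.** No arithmetic applies. The check compares current texts and looks for a reading that reconciles them.

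**1. Same trigger, different action.**

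| | Section 7.1.2 | Section 11.9 |
|---|---|---|
| Trigger | A condition in Section 11.9 is met | Any of criteria 1-5 is met |
| Action | Investigator considers stopping | Site stops drug |
| Timing | None given | Immediately (one later bullet says after monitoring) |
| Restart | Not addressed | Not allowed |

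**2. Does the discretion in 11.9 extend to stopping?** No. It covers referral to a specialist, who may decide on further tests or procedures.

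**3. Could 7.1.2 refer only to the group that may continue?** No. That group sits outside criteria 1-5 and goes back to the stop steps if it meets a criterion. Section 7.1.2 does not limit itself to that group, and its heading names the stopping criteria.

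**4. Is there a precedence rule?** None was found in the Protocol or the SAP.

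**5. How do the other rules in Section 7.1 that refer to an appendix behave, on whether drug stops?**

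| Rule | Main text | Appendix | Result |
|---|---|---|---|
| Liver | 7.1.2: consider stopping | 11.9: stop | Conflict |
| ECG | 7.1.3: may stop | 11.5: may stop | Agree |
| Exacerbation | 7.1.4: defers to 11.6 | 11.6.7: stop on a second or a severe event | No conflict |
| Pregnancy | 7.1.5: stop | 11.8: stop | Agree |

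Liver is the one mismatch among the four. The exacerbation row is weak evidence, because 7.1.4 states no action of its own and so could not disagree. The ECG row is more telling: where the protocol wants discretion, main text and appendix both say so.

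**6. Is 11.9 itself consistent?** On whether to stop, yes. On when, no: one bullet says at once and another says after liver monitoring is complete. Both are mandatory, so this second defect does not support the discretionary wording in 7.1.2.

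**The case against.** The best reply is that 7.1.2 works only as a pointer. It contains no thresholds, so an investigator must open 11.9 to learn whether a condition is met, and there the action list follows the criteria directly. The introduction to Section 7.1 also says that the circumstances listed may or may not lead to discontinuation, so mandatory and discretionary cases are mixed on purpose. The word used in 7.1.2 is conditions, not criteria 1-5, and 11.9 does describe one state in which drug continues. There are safeguards too: events meeting criteria 1-5 are reported within 24 hours, patients are recalled within 24 hours (criterion 1) or 24 to 72 hours (criteria 2-5), and Section 8.0 requires immediate safety concerns to be discussed with the sponsor at once.

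Part of this stands. An investigator is unlikely to act on 7.1.2 without seeing 11.9, and prompt reporting should bring a case of continued dosing to light quickly. The count of one mismatch in four describes drafting, not risk.

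The conflict remains for criteria 1-5. A reader who follows the cross-reference holds two incompatible instructions. The introduction to 7.1 allows optional rules but does not make the stop in 11.9 optional. The safeguards may detect a breach; they do not settle whether the investigator had a choice.

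**Conclusion.** The concern holds. For any patient meeting one of the five liver stopping criteria, 7.1.2 is wrong as written: it makes optional what 11.9 requires at once and for good. The conflict covers all five criteria.

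Its practical size cannot be stated in patients, because the documents give no expected liver event rate. Sample size, power and the type I error rate are unaffected.

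The conclusion rests on treating 11.9 as the governing text. The protocol does not say so, but 7.1.2 relies on 11.9 for its conditions, and 11.9 is the specific safety rule. This should be corrected as a patient-safety matter.

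**What to change.** Replace the sentence in 7.1.2 with two:

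> *Study medication must be stopped immediately, and not restarted, when any of liver chemistry stopping criteria 1-5 in Section 11.9 is met. It may also be stopped for other liver abnormalities if the Investigator judges this to be in the patient's best interest.*

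In the same document, delete the bullet in 11.9 that places discontinuation after the liver monitoring, so that the immediate stop stands alone. The documents do not explain that bullet, so the sponsor should confirm that it serves no other purpose before removing it.

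The drafting cost is one sentence replaced and one bullet deleted. SAP 17.5 shows that clarification letters were already used in this study for the COVID-19 withdrawal rule. Those letters clarified the meaning of a term, so the sponsor should decide whether a letter is enough here. A formal amendment needs ethics committee approval and, where applicable, regulatory approval (Protocol 11.2). No change to the SAP is needed.
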